Outcome:	Time to all-cause mortality (OS)		
Time (when follow up begins and ends):	From the day of treatment initiation until death or last observed clinical activity/last sign of the patient being alive or data cut-off, whichever occurred earlier		
Setting:	1L EGFRm+ metastatic NSCLC		
Main measure of effect:	Primary: Hazard ratio (95% CI) for overall survival		
	Secondary: median overall survival time (difference) in % (95% CI)		

The emulation of the main protocol elements of the FLAURA is illustrated side by side in **Table 2**.

Table 2. Trial emulation table summarizing the main protocol elements of the FLAURA trial and the planned emulation.

Protocol component	FLAURA RCT	Emulation	
Eligibility criteria	 - Age at least 18 years at time of randomization - Adenocarcinoma of the lung - Locally advanced or metastatic NSCLC, not amenable to curative surgery or radiotherapy - Tumour harbours one of the 2 common EGFR mutations known to be associated with EGFR-TKI sensitivity (Ex19del, L858R), either alone or in combination with other EGFR mutations - Patients must be treatment-naïve for locally advanced or metastatic NSCLC and eligible to receive first-line treatment with gefitinib or erlotinib 	there needs to be evidence of metastatic disease at time of treatment initiati (EDB4) - Evidence of any EGFR mutation in the 180 days before/on treatment initiati - Treatment needs to be first-line for advanced (EDB1) or metastatic (EDB2) disease or patients with prior exposure to any potential antineoplastic treatment	
Treatment	 World Health Organization Performance Status of 0 to 1 No prior treatment with any systemic anti-cancer therapy for locally advanced/metastatic NSCLC No prior treatment with an EGFR-TKI. osimertinib versus SoC EGFR-TKI (erlotinib or gefitinib) 	osimertinib versus SoC EGFR-TKI (erlotinib or gefitinib)	
strategies Assignment procedures	Random assignment to receive either osimertinib or SoC EGFR-TKI (gefitinib or erlotinib) in a 1:1 ratio	1:1 matching of patients based on their propensity to initiate osimertinib as opposed to SoC EGFR-TKI	
Follow-up period	Time from randomization until death from any cause or censoring of patients who did not die on the basis of the last recorded date that the patient was known to be alive	Time from treatment initiation until death from any cause or censoring of patients who did not die on the basis of the last recorded date that the patient was known to be alive	
Outcome	Overall survival	Overall survival	

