			Table 12)		
Practice type	dem_practice	edbx_get_demographics()	Setting patient is receiving care at	Nominal (academic, community, academic & community)	[-inf;0]
Socio-economic status	dem_ses	edbx_get_demographics()	Socioeconomic status (SES) index based on residence area of patient	Nominal (from '1 - Lowest SES' through '5 - Highest SES)	[-inf;0]
Smoking	c_smoking_history	edbx_get_demographics()	History of current or former (= TRUE) or never (= FALSE) smoking on or anytime before index date; if there are multiple records per patient, any evidence of former/current smoking is prioritized	Binary logical (TRUE, FALSE)	[-inf;0]
EGFR status	C_egfr_biomarker_status	edbx_get_biomarker()	Evidence of any EGFR mutation present. If patient has multiple measurements, any evidence of a mutation is prioritized. In case of ties, the closest measurement relative to index date is selected	Binary (negative, positive)	[-180;0]

Characteristic	Harmonized analysis variable name	R function to derive covariate (see pdf in appendix)	Details ¹	Variable encoding	Assessment window
ECOG	c_ecog	edbx_get_ecog()	ECOG performance status measured closest to index date within assessment window. In case of ties, the lower ECOG value is selected	Nominal (0, 1, 2, 3, 4); modelled as ordinal numeric in ROPRO ¹⁰ ; due to I/E criteria ECOG is modelled as a binary (0, 1) covariate	[-90;0]
Stage	c_stage_initial_dx	edbx_get_diagnosis_solid()	AJCC summary group stage at initial diagnosis	Ordinal numeric (from 0 to IV with sub-categories, e.g., IA1) ¹⁰	[-inf;0] at initial diagnosis of primary cancer
De novo metastatic status	c_de_novo_mets_dx	edbx_get_diagnosis_solid()	Evidence of presence of one or multiple metastases at/before initial diagnosis	Binary logical (TRUE, FALSE)	[-inf;0] at initial diagnosis of primary cancer
Evidence of metastases between initial diagnosis and index date	c_met_pre_index	edbx_get_diagnosis_solid()	Evidence of any metastasis between initial diagnosis and index date (includes the initial diagnosis and index date)	Binary logical (TRUE, FALSE)	[-initial dx;0]
Number of metastatic sites	c_number_met_sites	edbx_get_diagnosis_solid()	Number of metastatic sites for a given patient before/on index date	Integer	[-inf;0]
Time between initial diagnosis to index date	c_time_dx_to_index	edbx_get_diagnosis_solid()	Time in days between initial diagnosis to index date	Continuous	[-initial dx;0]

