Table 7. Primary and subgroup analysis specification

able 7. Primary and Subgroup	7 dilarysis specification
Hypothesis:	Initiation of osimertinib decreases the hazard of all-cause mortality as compared to initiation of erlotinib or gefitinib
Exposure contrast:	Initiation of osimertinib vs. initiation of erlotinib or gefitinib
Outcome:	Time to all-cause mortality (overall survival)
Databases used:	EDB1
Analytic software:	R 4.3.2. Version control of code and R packages will be established through git and Posit package manager, respectively. All packages are frozen to their most recent version as of April 24, 2024.
Model(s): (provide details or code)	See example code https://drugepi.gitlab-pages.partners.org/encore/flaura-nct-02296125/ (access only through MGB network for authorized personnel)
Confounding adjustment method	Name method and provide relevant details, e.g. bivariate, multivariable, propensity score matching (specify matching algorithm ratio and caliper), propensity score weighting (specify weight formula, trimming, truncation), propensity score stratification (specify strata definition), other. 1:1 propensity score nearest neighbor matching without replacement and a caliper of 1% of propensity score standard
Ministration of the	deviation
Missing data methods	Name method and provide relevant details, e.g. missing indicators, complete case, last value carried forward, multiple imputation (specify model/variables), other.
	Multiple imputation by chained equations using a random forest imputation model across all covariate types. The number of imputed datasets will be determined by the average proportion of missing values across all partially observed covariates. Imputation models will include all variables of the substantiative model, i.e., exposure, outcome, confounders/prognostic factors and additional auxiliary covariates.
Subgroup Analyses	List all subgroups
	In subgroup analysis, multiple imputation, propensity score matching and balance assessment will be conducted within each subgroup separately. The treatment effect will be estimated in the combined dataset by fitting a Cox proportional-hazards model that will include the exposure, the subgroup covariate of interest, and the treatment-by-subgroup interaction term. 1. Sex (Male, Female)
	2. Age (<65, ≥65)* 3. Resp (athricity (Agian Non Agian)*
	3. Race/ethnicity (Asian, Non-Asian)*4. Smoking history (current/former, never)5. ECOG (0, 1)*

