Sensitivity #6	Restrict to patients with Exon19 deletion only (databases for which this information is available)	FLAURA only included patients with sensitizing mutation (Exon19 deletion) but this information is not consistently provided across databases which is why in primary analyses we include all patients with any EGFR mutation assuming that it is sensitizing given that these patients initiated osimertinib, gefitinib or erlotinib	Target population is genetically more identical and increases specificity of biomarker measurement	Information not consistently available
Sensitivity #7	Re-weighting of strong risk factors and/or treatment effect modifiers distribution to match that of FLAURA	In the presence of effect modification, treatment effect estimates may be different if	Re-weighting adjusts for differences in distributions of key risk factors and/or	Re-weighting risk factors/potential

		the distribution of strong risk factors/effect modifiers is different in the emulated cohort versus the trial cohort	treatment effect modifiers (see subgroup analysis in Table 7)	effect modifiers to match the FLAURA trial and simultaneously balancing them across treatment groups may be challenging due to differences in measurement
Sensitivity #8	Including patients who have had at least 1 visit 90 days prior to treatment initiation	EHR are often lacking data continuity, and this analysis uses the requirement of 1 visit as a proxy for continuous observation periods	Considers aspect of data continuity	There may be patients who are put on treatment immediately in which case they are falsely excluded
Sensitivity #9	Exclusion of patients with osimertinib exposure before April 18, 2018	There are a few patients who are observed to have received osimertinib before its official approval (potentially due to off-label use in 1L, compassionate use, etc.)	Limits chances of exposure misclassification	May exclude truly eligible patients
Sensitivity #10	Restriction of eligible calendar time period from 2015 to 2022	Descriptive analyses indicate that there was a rapid uptake of new initiators of osimertinib immediately after approval in 2018 and a sudden decrease of SoC TKIs. This means there is hardly any overlap of patients pre/post 2018 and calendar cannot be sufficiently balanced	This sensitivity aims to mitigate the potential effects by imbalance in calendar time	Calendar time will overall remain imbalanced

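### Sensitivity analysis #6 restricts to Exon 19 deletion on the ground that FLAURA did, but Table 2 gives FLAURA's criterion as Ex19del or L858R

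*Protocol*

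**What the plan says.** Section 5, Table 2, FLAURA column, gives the trial's biomarker criterion: "Tumour harbours one of the 2 common EGFR mutations known to be associated with EGFR-TKI sensitivity (Ex19del, L858R"). It adds that the qualifying mutation could be present "either alone or in combination with other EGFR mutations". The emulation column replaces this with a broader rule, timed against the start of the study drug: "Evidence of any EGFR mutation in the 180 days before/on treatment". Section 6.6.7, Table 5, codes EGFR status as negative or positive and states: "If patient has multiple measurements, any evidence of a mutation is prioritized".

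Section 6.7.1, Table 9, sensitivity #6 is meant to narrow that rule. Its operational column reads "Restrict to patients with Exon19 deletion only (databases for which this information is available"). Its rationale is that "FLAURA only included patients with sensitizing mutation (Exon19 deletion) but this information is not consistently provided across databases", so the primary analysis takes every EGFR mutation and presumes it sensitizing because the patient started one of the study drugs. The strength claimed is "Target population is genetically more identical and increases specificity of biomarker measurement". The only limitation listed is that the information is not available in every database.

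**The concern.** Table 2 and Table 9 describe the eligibility rule of one and the same trial and give different rules. This is not a stray word in Table 9: the rationale names Exon 19 deletion alone, and the operational column then filters on it alone. An analyst programming from Table 9 would exclude every patient with L858R and no Ex19del, although Table 2 says such patients qualified for FLAURA.

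The purpose of #6 is to show whether admitting any EGFR mutation moves the estimate away from what FLAURA's own biomarker rule would give. That requires removing the non-qualifying mutations and nothing else. Because #6 removes a qualifying group as well, the plan's one check on its broad biomarker rule does not isolate that rule.

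**Working it through.** No figure in the plan needs reproducing. The check is a comparison of text, followed by a short argument about what #6 estimates.

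**Step 1. Divide the primary cohort by mutation.**

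| Group | Mutation | Primary rule | FLAURA rule (Table 2) | #6 (Table 9) |
|---|---|---|---|---|
| A | Ex19del, with or without others | in | in | in |
| B | L858R without Ex19del | in | in | **out** |
| C | neither | in | out | out |

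The check that is needed compares A+B+C with A+B. The check that is planned compares A+B+C with A. They differ by group B.

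**Step 2. What the planned comparison measures.** Let θ be the log hazard ratio in each group and w its share of the information, with wA + wB + wC = 1. Treat the pooled log hazard ratio as the information-weighted mean. This is an approximation that ignores re-matching and the non-collapsibility of the hazard ratio. Let θAB be the weighted mean over A and B.

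- Needed contrast: θAB − [(wA + wB)θAB + wC·θC] = wC(θAB − θC).
- Planned contrast: θA − [wA·θA + wB·θB + wC·θC] = wB(θA − θB) + wC(θA − θC).

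The planned contrast carries the extra term wB(θA − θB), which has nothing to do with the any-mutation rule. If the result moves, either term may be the cause. If it does not move, both terms may be small or they may offset. The two contrasts coincide when wB = 0 or θA = θB, that is, when no such L858R patients are present or the treatment effect is the same in Ex19del and L858R patients. The plan states neither.

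**Step 3. Does another planned analysis fill the gap?** Counting in the protocol text:

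- Table 9 has 12 sensitivity analyses; 1 (#6) restricts on mutation type.
- Table 7 has 5 subgroups (sex, age, race/ethnicity, smoking, ECOG); 0 are by mutation type.
- Table 5 has 1 EGFR variable, which does not separate mutation types.
- Sensitivity #7 points to the Table 7 subgroups for its effect modifiers, and Section 7 describes it in terms of race and smoking.
- L858R is named only in Table 2.

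No planned analysis in the protocol text applies FLAURA's biomarker criterion.

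**Step 4. Size.** The precision lost by dropping group B depends on wB and on the number of events. The text gives neither: Section 10.3 states 80% power at a hazard ratio of 0.8 without an event count, the figure there is not readable, and no mutation split is reported. Table 9 also does not say which databases would enter #6. No number can therefore be attached to the loss or to the direction of a shift.

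**The case against.** The contradiction itself is hard to dispute; the case on the other side concerns its reach.

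- *Every patient #6 keeps is FLAURA-eligible.* True, and so the claimed gain in biomarker specificity is real. An unchanged hazard ratio in a wholly eligible subset is some reassurance. It is not clean attribution, because the two terms in the planned contrast can offset.
- *Data availability may explain the choice.* Table 9 uses availability to justify the broad primary rule and to limit which databases enter #6. It does not say that L858R is unrecorded where Ex19del is recorded. Even if that were so, the description of FLAURA would still be wrong and the limitations column would still omit the loss of L858R.
- *The operational detail may sit elsewhere.* Sections 6.6.2 and 6.6.3 refer to Excel appendix tables, and Table 5 to code documentation, none of which is at hand. They may settle how #6 will be run. They cannot reconcile two tables in the body of the protocol.
- *Tables 5 and 7 prove little.* This stands in part. Table 5 lists key covariates and has no Ex19del variable either, so it says nothing about whether L858R is recorded. The absence of a mutation-type subgroup is not in itself an error. These tables show only that nothing else in the text does the job of #6; the finding rests on Table 2 against Table 9.

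**Conclusion.** The concern holds. Table 9 misstates FLAURA's criterion relative to Table 2, and #6 is built on the misstatement. As written it tests an incomplete subset of the FLAURA biomarker population and cannot isolate the effect of admitting any EGFR mutation, unless the treatment effect is the same in Ex19del and L858R patients or the cohort has no L858R patients without Ex19del.

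The reach is limited: 1 of 12 sensitivity analyses, with no effect on the primary cohort, the primary hazard ratio or the stated power. It should be corrected but does not threaten the main result. The conclusion assumes only that Table 2 states FLAURA's rule as the authors intend it; precision loss and direction of bias are left unquantified.

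**What to change.** 1. Rewrite the rationale of #6 so that it gives the same FLAURA criterion as Table 2.
2. Check, database by database, whether L858R is recorded.
3. Where both mutations are recorded, restrict #6 to documented Ex19del or L858R, alone or with other EGFR mutations. Ex19del-only may be kept as an optional stratum, labelled as such.
4. Where L858R is not recorded, relabel #6 as an Ex19del-only analysis and add the exclusion of L858R patients to its limitations column.

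The cost is one corrected table row and the availability check, plus a changed filter where the data allow. If no database records L858R, only the rationale, label and limitation change.

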While the MAR assumption is a strong assumption to hold across all considered covariates, it was shown that especially in the context of partially observed covariate data (as opposed to missing exposure and outcome data), only mechanisms in which a covariate causes its own missingness leads to critical bias (MNAR).²³ In such situations, multiple imputation can have significant advantages over a complete case analysis since additional information (auxiliary covariates and missing indicator variables) can be included in imputation algorithms which can make the MAR assumption holding more plausible and increase efficiency in treatment effect estimates since all patients and critical covariates can be retained and variances can be realistically estimated, considering both the general sampling error and the error introduced by missing data.^{24,25} Hence, multiple imputation with flexible, non-parametric random forest imputation algorithms²⁶ (mice R package²⁷) will be used for this trial emulation. The number of imputed datasets (*m*) will be determined for each database separately based on the average proportion missingness observed in the analytic cohort and results from the above-referenced missing data investigations will inform the choice of appropriate sensitivity analyses.

Figure 5. Covariate balance across imputed datasets (simulated example).

Covariate Balance

Range across imputations

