To estimate the treatment effects for osimertinib using propensity score matching across imputed datasets we will apply the "within" approach using the "MatchThem" R package. 28,29 That is, propensity score matching and the estimation of the treatment effect are performed in each imputed dataset separately and resulting treatment effect estimates are combined using Rubin's rule. In this study, this will be implemented by matching eligible patients on their propensity to initiate osimertinib using a 1:1 nearest neighbor matching algorithm without replacement and a caliper of 1% of the standard deviation of the propensity score. The resulting covariates balance will be assessed by computing and visualizing ASMDs before and after matching across datasets. As compared to a single dataset matching approach, this can lead to a range of ASMDs per covariate due to random variation across imputed datasets for which an example (using simulated data) is illustrated in Figure 5. If sufficient balance can be established, a Cox proportional hazards regression model will be fit to estimate the marginal average treatment effect in the matched population. Since in most databases there are more osimertinib patients than patients in the control arm, the estimand will rather correspond to the ATC than the ATT. Confidence intervals will be estimated using cluster-robust standard errors. 30 As a secondary endpoint, we will additionally estimate the median OS survival time difference between the two exposure groups using the Kaplan-Meier method. It should be noted that due to administrative and de-identification purposes, the date of death is often only available at the month- or year-granularity level, in which case the date of death will be imputed to the 15th of a month or July 2nd of a year, respectively (depending on the database). In rare cases, this can lead to negative/implausible follow-up times if the date of death is very close to the index date. These patients will be excluded from the analysis.

The final hazard ratio and median OS survival time difference estimates for each database will then be combined using Rubin's rule.^{27,31} To arrive at a single estimate across databases, the final estimates will be summarized through a meta-analytic fixed effects model.³² A summary of the analytic approach is summarized in Table 7 and an example workflow with simulated data and annotated code can be found https://example.com/here/beta-arrive

A. Primary analysis

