Sensitivity #11	Addition of EDB2 and EDB4	EDB2 and EDB4 are not considered in primary analyses for reasons given in section 6.1.1.	Increased sample size and potentially broader coverage of general US cancer population	See limitations listed in section 7.

Sensitivity #12	Missingness is handled by restricting to patients with complete observations on a subset of the most important confounders ("complete cases")	Instead of imputing data, this sensitivity analysis restricts the analysis cohort to patients with complete observations on key confounders	Data will not be imputed and missingness is assumed to be missing completely at random	The restriction to complete cases will significantly decrease sample size. To limit the attrition of patients with partially observed covariates, it won't be possible to use all covariates used in the main analysis propensity score model, but only consider key covariates with overall low proportions of missingness (age, sex, etc.)
-----------------	---	--	--	--

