6.8. Study size and feasibility

See appendix 4 (first feasibility matching on age, sex, comorbidity score) and appendix 5 (second feasibility matching on all predefined propensity score variables). Propensity score distribution plots with c-statistics are available in appendix 6. Table 1 showing prevalence of baseline characteristics and standardized differences in distribution are available in appendix 7.

7. Limitation of the methods

- Missingness in prognostic factors is a major challenge which is addressed in this emulation by multiple imputation using a non-parametric imputation algorithm. Multiple imputation usually assumes that missingness can be explained by observed characteristics, which may be empirically evaluated using principled missingness diagnostics, but the true underlying missingness mechanisms are usually unknown. Nevertheless, multiple imputation makes use of additional information (auxiliary covariates) which can render the underlying missingness assumptions more plausible. In addition, assumptions for alternative missing data approaches like complete case analysis or the "missing indicator approach" come with even stronger assumptions and additionally have the limitation of significantly reduced sample sizes, especially when comprehensively adjusting for known confounders and prognostic factors.
- Data continuity is a major challenge in EHR databases since "guaranteed" observable periods (such as continuous enrolment periods in administrative claims data) do not exist which may lead to measurement error in key covariates and exposure misclassification. Sensitivity analysis #8 tries to address this requiring patients to have had at least one visit before the index date which increases the likelihood that a patients was not only diagnosed at the respective center but is also regularly seen.

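### Sensitivity #12 drops imputation and shrinks the propensity score set at the same time, so its difference from the primary HR cannot be attributed to either change

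*Protocol*

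**What the plan says.** The primary analysis (Protocol 6.7.1, Table 7) handles missing covariates by "Multiple imputation by chained equations using a random forest imputation model across all covariate types". Within each imputed dataset it then applies a "1:1 nearest neighbor matching algorithm without replacement and a caliper of 1% of the standard deviation of the propensity score", fits a Cox model for a marginal effect in the matched population, and pools the results.

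The Sensitivity #12 row of Table 9 has four relevant cells:

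- **What is varied:** "Missingness is handled by restricting to patients with complete observations on a subset of the most important confounders".
- **Why:** the cell contrasts restriction to complete observations with imputing. It names no other change.
- **Strengths:** "Data will not be imputed and missingness is assumed to be missing completely at random".
- **Limitations:** the sample shrinks, and to limit attrition "it won't be possible to use all covariates used in the main analysis propensity score model". The analysis will "only consider key covariates with overall low proportions of missingness (age, sex, etc".).

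Two other places bear on this. In 6.7.1, after discussing covariates that cause their own missingness, the protocol says "In such situations, multiple imputation can have significant advantages over a complete case analysis", citing auxiliary information and efficiency. Section 7 says that alternatives such as complete-case analysis "come with even stronger assumptions and additionally have the limitation of significantly reduced sample sizes".

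**The concern.** A sensitivity analysis is informative when it changes one assumption and leaves the rest alone. Sensitivity #12 changes three things: the missing-data method, the patients analysed, and the covariates in the propensity score. If its HR differs from the primary HR, a reader cannot tell whether imputation mattered or whether confounders were left unadjusted. If the two agree, opposing shifts may have offset each other.

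The selection rule also works against the purpose. The row promises the most important confounders but picks covariates for low missingness, and imputation has least influence on exactly those. Section 6.6.7 describes labs and vitals as highly prognostic, and section 7 calls missing prognostic factors a major challenge. A low-missingness rule tends to exclude partly observed factors of that kind.

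Sensitivity #12 is the only row of Table 9 whose stated purpose is to replace imputation. As specified, it cannot answer that question.

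**Working it through.** **1. The comparison as planned.** Let P be the primary log HR (imputed, full set), C the log HR from #12 (complete cases, reduced set), and M the log HR from an imputed run on the reduced set. Then

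C − P = (M − P) + (C − M)

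The first bracket is the effect of the covariate set. The second is the effect of missing-data handling, including the change of cohort. The protocol yields P and C but not M, so only the sum is seen.

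**2. Can the first bracket dominate?** The protocol gives no missingness proportions, covariate effects or HR for #12, so there is no protocol figure to reproduce. An illustrative simulation used these inputs, all assumed except the matching method and the HR:

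- 60 runs of n = 3000.
- x1 always observed; x2 missing in about 40% of patients.
- Treatment logit 0.5 + 0.3·x1 − 0.5·x2.
- Log hazard ratio terms ln(0.8)·treatment + 0.3·x1 + 0.5·x2.
- 1:1 nearest-neighbour matching without replacement, caliper 0.01 SD of the propensity score, then Cox.

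The full cohort with nothing missing stands in for imputation that works perfectly. The simulation contains no imputation step.

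| Missingness of x2 depends on | Full cohort, x1+x2 | Complete cases, x1+x2 | Full cohort, x1 only | Complete cases, x1 only |
|---|---|---|---|---|
| nothing (MCAR) | 0.830 | 0.824 | 0.668 | 0.665 |
| x1 and treatment | 0.820 | 0.826 | 0.669 | 0.665 |
| x2 itself | 0.834 | 0.846 | 0.676 | 0.692 |
| the outcome | 0.809 | 0.705 | 0.665 | 0.557 |

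The Monte Carlo SE of each mean log HR is 0.007 to 0.011. Applying the split in step 1:

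| Scenario | Covariate set | Missing-data handling | Sum (what #12 shows) |
|---|---|---|---|
| MCAR | ln(0.668/0.830) = −0.217 | ln(0.665/0.668) = −0.005 | −0.222 |
| x1 and treatment | ln(0.669/0.820) = −0.204 | ln(0.665/0.669) = −0.006 | −0.210 |
| x2 itself | ln(0.676/0.834) = −0.210 | ln(0.692/0.676) = +0.023 | −0.187 |
| outcome | ln(0.665/0.809) = −0.196 | ln(0.557/0.665) = −0.177 | −0.373 |

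Under MCAR, restricting to complete cases does no harm by construction, yet #12 would sit −0.222 from the primary. That is about the size of the target effect itself, ln(0.8) = −0.223. In the own-value scenario the two brackets have opposite signs, although +0.023 is near the limit of simulation error.

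**3. The MCAR statement.** With x1 and x2 both in the model, complete cases against the full cohort gave 0.824 vs 0.830 (MCAR), 0.826 vs 0.820 (x1 and treatment), 0.846 vs 0.834 (own value) and 0.705 vs 0.809 (outcome). Only outcome-dependent missingness produced a clear shift. MCAR is therefore sufficient but was not necessary in these settings. It is a restriction, and section 7 treats complete-case assumptions as the stronger ones, so it does not belong under strengths.

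**4. Precision of a complete-case run with more covariates.** Section 10.3 states 80% power at HR 0.8, two-sided alpha 0.05, by Schoenfeld's method. The event count is not in the text. Inverting the formula gives 4 × (1.960 + 0.842)² / (ln 0.8)² ≈ 631 events. If complete cases kept 75%, 50% or 25% of these (an assumed range), power would be 68%, 51% or 29%. At 50% (about 316 events) the SE of the log HR is 2/√316 = 0.11. By a nested-sample approximation, the SE of its difference from the full cohort is √(4/316 − 4/631) = 0.08.

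**The case against.** **Disclosure.** The protocol lists the reduced set under limitations and gives attrition as the reason. That is fair, but it presents the smaller set as a trade-off. It does not say that the comparison with the primary then cannot be interpreted, and it names no comparator.

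**SAP detail.** The exact subset could be left to an SAP. The protocol itself, however, fixes the low-missingness rule and lists the runs.

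Several stronger readings are tempting, and the documents do not support them:

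- *The protocol claims that complete cases require MCAR.* It says MCAR is assumed. For a marginal effect in a matched population, MCAR is also a simple condition for complete cases to represent the same patients. The assumption is restrictive and sits in the wrong column, but it is not an error.
- *Bias from data missing not at random (MNAR) would go unnoticed.* Sensitivity #5 is a delta-imputation tipping-point analysis for this purpose, and the Group 3 diagnostics in Table 6 look for it. Sensitivity #12 is not the protocol's MNAR safeguard.
- *ECOG and labs will be dropped.* The row names only age and sex. Labs are plausible casualties, but without missingness proportions the excluded covariates are unknown.
- *The 6.7.1 and section 7 remarks favouring imputation are wrong.* The first is hedged and rests on auxiliary information and efficiency. The second is too broad as a general ranking, but section 7 also concedes that the true mechanisms are usually unknown.
- *A difference in a fuller complete-case run should trigger Sensitivity #5.* In a separate illustration with one strong confounder 39% missing by its own value, imputation under missing at random gave 0.764 and complete cases with that confounder 0.797, a log difference of −0.04. Against an SE of 0.08 that is about half a standard error, so a trigger would mostly follow noise.

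**Conclusion.** The point holds on the design of Sensitivity #12 alone. The covariate set changes together with the missing-data method and the cohort, and no listed run separates them. A difference from the primary HR cannot be attributed to imputation, and agreement is weak reassurance. This follows from the Table 9 row and does not depend on the simulation.

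The simulated sizes show only that the covariate-set effect can outweigh the effect #12 is meant to reveal. They rest on one confounder, wholly omitted, with no correlated or auxiliary covariates, whereas the primary model has many covariates and its imputation uses auxiliaries. The primary HR is unaffected. This is a cheap improvement to one of twelve sensitivity analyses.

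**What to change.** 1. Add a multiple-imputation run with the same matching on the identical reduced covariate set. Primary against imputed-reduced then shows the effect of the covariate set. Imputed-reduced against complete-case-reduced shows the effect of missing-data handling.
2. Where numbers permit, add a complete-case run that includes the key partly observed prognostic factors, paired with imputation on that same set. Report it descriptively with its confidence interval.
3. Keep Sensitivity #5 unconditional.
4. In Table 9, move the MCAR statement from strengths to limitations, and note that MCAR is sufficient but not always necessary for a complete-case analysis.

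The cost is two or three extra runs and a few lines of text. The runs in item 1 need no new data. The complete-case run in item 2 will have a smaller sample and a wider interval.
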